3. PATIENT SELECTION

3.1 Eligibility Criteria

- 3.1.1 Patients must have pathologically (histologically or cytologically) proven diagnosis of head and neck squamous cell carcinoma (HNSCC) involving the oral cavity, oropharynx, larynx, hypopharynx, paranasal sinuses or unknown primary squamous carcinoma limited to the head and neck region;

- Cohort 1: Unresectable locally advanced non-nasopharyngeal SCCHN without evidence of distant metastases
- Cohort 2: Patients with non-nasopharyngeal SCCHN who have undergone gross total surgical resection within 63 days prior to registration. Patients must have at least 1 of the following high-risk pathologic features: extracapsular nodal extension, invasive cancer at the primary tumor resection margin (positive margin), lymphovascular invasion or perineural invasion, or the presence of multilevel nodal disease. Patients must be without evidence of distant metastases.

3.1.2 Women of childbearing potential and male participants who are sexually active must agree to use a medically effective means of birth control.

3.1.3 Cohort 1: Patients in Cohort 1 must have either (a) measurable disease, defined as at least one lesion that can be accurately measured in at least one dimension (longest diameter to be recorded for non-nodal lesions and short axis for nodal lesions) as ≥ 20 mm (≥ 2 cm) with conventional techniques or as ≥ 10 mm (≥ 1 cm) for non-nodal lesions, and > 15 mm (> 1.5 cm) for nodal lesions with spiral CT scan, MRI, or calipers by clinical exam or (b) evaluable disease based on evaluable non-target lesions (< 1.5 cm - > 1.0 cm) as specified in protocol section 11.1.1. See Section 11 for the evaluation of measurable disease.

Cohort 2: Subjects in the post-operative setting (Cohort 2) are not required to have measurable disease and response rate will not be assessed in cohort 2.

Date of resection: _____

3.1.4 Patients may have a history of prior head and neck malignancy, but must be able to tolerate full dose radiation and chemotherapy for the current head and neck cancer, as determined by the treating oncologist.

3.1.5 Age ≥ 18 years.

3.1.6 ECOG performance status 0, 1 or 2 (see Appendix A).

3.1.7 Life expectancy of greater than 12 weeks.

3.1.8 Patients must have normal organ and marrow function assessed within 14 days prior to registration as defined below:

- absolute neutrophil count $\geq 1,000/\text{mcL}$
- platelets $\geq 100,000/\text{mcL}$
- creatinine within normal institutional limits

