- creatinine clearance $\geq 60 \text{ mL/min}/1.73 \text{ m}^2$ for patients with creatinine levels above institutional normal

OR

- 3.1.9 No prior chemotherapy for the **current** locally advanced SCCHN is allowed. Prior radiation or chemotherapy for a previous head and neck cancer is allowed provided full dose cisplatin and radiation can be delivered to the patient in this clinical trial and provided the patient is in remission from the prior head and neck cancer, and can undergo full dose radiation and chemotherapy for the current primary head and neck cancer.
- 3.1.10 Cisplatin and radiation are known teratogens. For this reason, women of child-bearing potential and men must agree to use adequate contraception (hormonal or barrier method of birth control; abstinence) prior to study entry, throughout the duration of active treatment and for 4 months after completion of chemotherapy and radiation. Should a woman become pregnant or suspect she is pregnant while she or her partner is participating in this study, she should inform her treating physician immediately. Men treated or enrolled on this protocol must also agree to use adequate contraception prior to the study, for the duration of active study treatment, and for 4 months after completion of chemotherapy and radiation (both induction and definitive) administration.

- 3.1.11 Ability to understand and the willingness to sign a written informed consent document.

3.2 **Exclusion Criteria**

- 3.2.1 Patients who have had chemotherapy or radiotherapy within 4 weeks (6 weeks for nitrosoureas or mitomycin C) prior to entering the study or those who have not recovered from adverse events due to agents administered more than 4 weeks earlier.
- 3.2.2 Patients who are receiving any other investigational agents.
- 3.2.3 History of allergic reactions attributed to compounds of similar chemical or biologic composition to cisplatin.
- 3.2.4 Patients with greater than grade 2 hearing loss.
- 3.2.5 No other prior malignancy is allowed except for the following: head and neck cancer in remission, adequately treated basal cell or squamous cell skin cancer, in situ cervical cancer, adequately treated previous Stage I or II cancer from which the patient is currently in complete remission or other cancer from which the patient has been disease-free for 2 years.
- 3.2.6 Patients with nasopharynx or salivary gland primary site.

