5.2.2 Cisplatin Dosing

Use the actual body weight as long as the BSA is ≤ 2.3 . If the BSA is > 2.3 , recalculate using the adjusted body weight, and use the recalculated BSA to determine the dose with no cap.

Estimate Ideal body weight in (kg)

Males: IBW = 50 kg + 2.3 kg for each inch over 5 feet

Females: IBW = 45.5 kg + 2.3 kg for each inch over 5 feet

Adjusted body weight

$$AjBW = IBW + 0.4(ABW - IBW)$$

Arm 1 – Conventional fractionation plus every 3-week cisplatin

Patients will receive cisplatin (100 mg/m²) administered intravenously over 1 hour on days 1, 22, and 43 of the treatment course, relative to the initiation of radiation.

Arm 2 – Conventional fractionation plus weekly cisplatin

Patients will receive cisplatin (40 mg/m²) administered intravenously over 1 hour on days 1, 8, 15, 22, 29, 36, and 43 of the treatment course, relative to the initiation of radiation.

Premedication: Arms 1 & 2

Suggested premedication: include aprepitant (intravenous or oral), ondansetron, dexamethasone and either promethazine or prochlorperazine, per institutional standard. This trial endorses the NCCN guidelines for anti-emetic prophylaxis.

Pre- and Post-hydration: Arms 1 & 2

Patients must receive vigorous hydration and diuresis. A suggested regimen is: pre-hydration with a 1 liter of normal saline with electrolyte supplementation (e.g. potassium, magnesium) per standard of care, over 2 hours i.v. immediately prior to cisplatin. Then cisplatin 100 mg/m² in 500 ml normal saline is administered over 1 hour. Following cisplatin infusion, an additional 1 liter of normal saline with electrolyte supplementation (e.g. potassium, magnesium) per standard of care, given post-hydration over 2 hours.

Please see Section 6.0 for all dose modifications of cisplatin.

5.3 **Radiation Therapy**

All radiation therapy is considered standard of care, and toxicities and dose modifications will be made by the treating physician based on institutional standards. The guidelines below are recommended practice but may be modified at the discretion of the treating radiation oncologist.

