6. DOSING DELAYS/DOSE MODIFICATIONS

Dose Modifications for cisplatin, days 8 and beyond

Dose Level	Every 3-week Cisplatin	Weekly Cisplatin
-2	50 mg/m ² every 3 weeks	20 mg/m ² weekly
-1	75 mg/m ² every 3 weeks	30 mg/m ² weekly
0	100 mg/m ² every 3 weeks	40 mg/m ² weekly

No more than two dose reductions are allowed and no re-escalation of dosing is allowed. If a subject requires more than two dose reductions, cisplatin will be permanently discontinued. Every effort will be made to complete all planned doses of chemotherapy, with dose modifications listed below, however, no chemotherapy will be given after completion of radiation.

Neutropenia. If on the day of scheduled treatment with cisplatin the absolute neutrophil count (ANC) is < 1000, hold treatment until ANC ≥ 1000 then treat at 100% dose.

Neutropenic fever. If grade 3 or 4 neutropenic fever occurs, defined as temperature ≥38.5°C [101°F] sustained for more than one-hour concomitant with ANC <500/mm³, hold cisplatin until ANC >1000, and reduce subsequent cisplatin doses by 1 dose level.

Thrombocytopenia. If on the day of scheduled treatment with cisplatin the platelet count is <75,000 hold treatment until platelets are >75,000 then treat at 100% dose.

Thrombocytopenia that results in significant bleeding. If grade 3 or 4 thrombocytopenia occurs with bleeding that is clinically significant, as determined by the treating physician, hold cisplatin until platelets are >75,000 and reduce subsequent cisplatin doses by 1 dose level.

Neurotoxicity. If grade 3 or greater neurotoxicity, including neuropathy occurs, hold cisplatin until resolution to less than or equal to grade 1. Resume cisplatin at one dose level lower. If grade 3 or greater neurotoxicity persist after two dose reductions or does not improve after 14 days, discontinue cisplatin.

Renal Toxicity. If a subject's creatinine clearance falls below 50 ml/min, cisplatin should be held for that dose and should only be restarted once the creatinine clearance improves to >50 ml/min. Subsequent doses should be dose reduced by one dose level. If Cr Cl does not recover to >50 ml/min after 14 days, discontinue cisplatin.

Mucositis: If grade 4 mucositis occurs, hold cisplatin until resolution to less than or equal to grade 2 and reduce subsequent cisplatin doses by 1 dose level.

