7.1 Expected Toxicities

7.1.1 Adverse Events List(s)

7.1.1.1 Adverse Event List(s) for Cisplatin

Please see the package insert for all toxicities associated with CISPLATIN. Below is a listing of the most commonly seen toxicities.

Nephrotoxicity: Dose-related and cumulative renal insufficiency, including acute renal failure, is the major dose-limiting toxicity of PLATINOL. Renal toxicity has been noted in 28% to 36% of patients treated with a single dose of 50 mg/m². It is first noted during the second week after a dose and is manifested by elevations in BUN and creatinine, serum uric acid and/or a decrease in creatinine clearance. Renal toxicity becomes more prolonged and severe with repeated courses of the drug. Elderly patients may be more susceptible to nephrotoxicity. Impairment of renal function has been associated with renal tubular damage. The administration of CISPLATIN using a 6-8-hour infusion with intravenous hydration, and mannitol has been used to reduce nephrotoxicity. However, renal toxicity still can occur after utilization of these procedures.

Ototoxicity: Ototoxicity has been observed in up to 31% of patients treated with a single dose of CISPLATIN 50 mg/m² and is manifested by tinnitus and/or hearing loss in the high frequency range (4000 to 8000 Hz). Decreased ability to hear normal conversational tones may occur. Deafness after the initial dose of CISPLATIN has been reported. Ototoxic effects may be more severe in children receiving CISPLATIN. Hearing loss can be unilateral or bilateral and tends to become more frequent and severe with repeated doses. Ototoxicity may be enhanced with prior or simultaneous cranial irradiation. It is unclear whether CISPLATIN-induced

ototoxicity is reversible. Ototoxic effects may be related to the peak plasma concentration of CISPLATIN. Careful monitoring of audiometry is recommended prior to initiation of therapy and prior to subsequent doses of CISPLATIN. Vestibular toxicity has also been reported. Ototoxicity may become more severe in patients being treated with other drugs with nephrotoxic potential.

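### With normal serum creatinine, no clearance limit is clearly required before the day 1 cisplatin dose, although later doses are held below 50 ml/min

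*Combined protocol and SAP*

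**What the plan says.** Section 3.1.8 offers two renal routes to eligibility. The first is "creatinine within normal institutional limits", with no clearance value. The second is a clearance of at least 60 mL/min/1.73 m², and it applies only "for patients with creatinine levels above institutional normal". The stray OR printed after these bullets appears to belong between them and does not change the reading. Section 3.1 sets no upper age limit and no minimum weight.

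Section 5.2.2 gives Arm 1 cisplatin 100 mg/m² "administered intravenously over 1 hour on days 1, 22, and 43 of the treatment course", and Arm 2 40 mg/m² weekly from day 1. Neither arm's text has a renal condition. It adds "Patients must receive vigorous hydration and diuresis" and ends "Please see Section 6.0 for all dose modifications of cisplatin".

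Section 6 opens with "Dose Modifications for cisplatin, days 8 and beyond", then the dose-level table, then the toxicity rules. Under the renal rule, if "creatinine clearance falls below 50 ml/min, cisplatin should be held for that dose"; treatment resumes above 50 one dose level lower, and cisplatin stops if there is no recovery after 14 days.

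Neither 3.1.8 nor Section 6 names a formula. The first uses mL/min/1.73 m², the second ml/min. The Section 10 calendar lists serum creatinine (through its chemistry panels) before study and in week 1, but no clearance.

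**The concern.** The protocol treats a clearance below 50 ml/min as too low for a scheduled dose, yet appears not to ask for that value before the first dose when serum creatinine is normal. In Arm 1 the first dose falling under the Section 6 heading is day 22, after a full 100 mg/m² has been given.

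What is at stake is patient safety. Section 7.1.1.1 states: "Dose-related and cumulative renal insufficiency, including acute renal failure, is the major dose-limiting toxicity". It also says that older patients may be more prone to it. Serum creatinine depends on muscle mass, so an older or light patient can have a normal value and a low clearance.

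**Working it through.** The plan states no figure on this point, so there is none to reproduce. Nothing here enters the sample-size calculation in 13.2.

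**Step 1. Which rule reaches day 1 when creatinine is normal?**

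| Place | Clearance limit on day 1? |
|---|---|
| 3.1.8, normal creatinine | None |
| 3.1.8, raised creatinine | 60 mL/min/1.73 m² |
| 5.2.2 and 8.1, dosing and hydration | None |
| 6, renal rule | 50 ml/min, under a line limited to day 8 onward |
| 10, calendar | Creatinine measured; clearance not listed |

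**Step 2. Can normal creatinine go with a clearance below 50?** The documents give no formula, no institutional upper limit, and no age or weight distribution. The formulas and patients below are therefore assumptions.

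- Cockcroft-Gault (CG), ml/min: (140 − age) × kg / (72 × creatinine), × 0.85 for women.
- CKD-EPI 2021, mL/min/1.73 m²: 142 × min(cr/k, 1)^a × max(cr/k, 1)^−1.2 × 0.9938^age, × 1.012 for women; k = 0.7 and a = −0.241 for women, k = 0.9 and a = −0.302 for men.
- CKD-EPI in ml/min: the indexed value × BSA/1.73, with BSA = √(cm × kg/3600).

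Creatinine (mg/dL) above which clearance is below 50. For CG, set clearance to 50 and solve; 72 × 50 = 3600.

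- Woman 75 y, 50 kg: 65 × 50 × 0.85 / 3600 = 0.77
- Woman 70 y, 55 kg: 70 × 55 × 0.85 / 3600 = 0.91
- Man 75 y, 60 kg: 65 × 60 / 3600 = 1.08

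The CKD-EPI values were solved numerically.

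| Assumed patient | CG, ml/min | CKD-EPI, ml/min | CKD-EPI, per 1.73 m² |
|---|---|---|---|
| Woman 75 y, 50 kg, 158 cm | 0.77 | 1.01 | 1.14 |
| Woman 70 y, 55 kg, 158 cm | 0.91 | 1.07 | 1.17 |
| Man 75 y, 60 kg, 170 cm | 1.08 | 1.42 | 1.46 |

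**Step 3. Clearance at given creatinine values.**

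| Assumed patient, creatinine (mg/dL) | CG, ml/min | CKD-EPI, ml/min | CKD-EPI, per 1.73 m² |
|---|---|---|---|
| Woman 75 y, 50 kg, 158 cm, 0.9 | 42.6 | 57.1 | 66.7 |
| Same, 1.1 | 34.9 | 44.9 | 52.4 |
| Same, 1.2 | 32.0 | 40.4 | 47.2 |
| Man 75 y, 60 kg, 170 cm, 1.1 | 49.2 | 68.1 | 70.0 |

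The first row by CG: 65 × 50 × 0.85 / (72 × 0.9) = 2762.5 / 64.8 = 42.6.

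**Step 4. Who is outside the gap.** A man of 60 y, 70 kg, creatinine 1.2 mg/dL has 80 × 70 / (72 × 1.2) = 64.8 ml/min by CG.

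Under CG the gap includes creatinine values that would commonly be called normal. Under CKD-EPI it narrows to cases such as older, light women at about 1.1 to 1.2 mg/dL, and only if the institution counts that as normal.

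**The case against.** The strongest reply is about the heading. The day 8 line sits directly above the dose-level table and may be only its caption. The title of Section 6 has no day limit, and neither does the renal rule. Section 5.2.2 refers to Section 6 right after listing the day 1 dose. If the line is a caption and 50 is an absolute level, day 1 is covered. This stands in part. A reader might infer that no rule covers day 1 on any reading; the documents do not support that. But the rules do follow that line, and the verb in the renal rule can mean a decline on treatment, so day 1 coverage cannot be relied on.

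Second, there are general safeguards. Section 3.1.4 lets the treating oncologist judge whether full-dose treatment is tolerable, creatinine is measured at screening and in week 1, and the package insert is cited. The 3.1.4 judgement is in the criterion on prior head and neck cancer and has no renal value. The package insert was not available for this review. What is missing is a required clearance calculation, not a creatinine test.

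Third, the size rests on assumptions. This stands. The patients are illustrative, and the 75-year-old woman at 0.9 mg/dL is at 66.7 in the unit that 3.1.8 uses.

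A reader might also infer that investigators would decide differently on the same patient. Screening is at one centre (4.2), and nothing shows that its clinicians use different formulas.

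**Conclusion.** The point holds as a first-dose safety gap in the text as most naturally read, and as an ambiguity if the day 8 line is only a caption. For patients with normal creatinine, 3.1.8 sets no clearance limit and the 50 ml/min hold does not clearly reach day 1. Some older or lighter patients can therefore receive full-dose cisplatin at a clearance at which a later dose would be held.

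The number affected cannot be derived from the documents; it depends on the formula, the institutional limit and the patients enrolled. A reader might infer an effect on power, on the comparison of arms or on cisplatin delivery. None is shown: the gap applies to both arms and changes no input in 13.2. It should be fixed because the remedy is cheap and concerns the toxicity that the protocol itself ranks first. Confidence is medium.

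**What to change.** **In 3.1.8:** require a calculated creatinine clearance of at least 50 ml/min for every patient, from the screening creatinine, before randomization. Name one formula, for example Cockcroft-Gault in ml/min, which matches the Section 6 unit. Restate the existing threshold of 60 for raised creatinine in the same formula and unit. Patients at 50 to 60 ml/min with normal creatinine stay eligible.

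**In Section 6:** state that 50 ml/min is an absolute level and that the renal hold also applies to day 1, using the week 1 creatinine. A randomized patient held on day 1 follows the existing hold, 14-day and dose-reduction rule and stays in the assigned arm for analysis. Because 5.2.1 asks for radiation and cisplatin to start within a day of each other, say also whether radiation starts on schedule for such a patient.

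**Cost:** a short amendment and no new test, since creatinine, weight, height and demographics are already collected. The week 1 creatinine must be available before the first infusion. Patients with normal creatinine and clearance below 50 become ineligible; they are probably few, but the number is unknown and depends on the formula. Restating the 60 threshold without indexing makes it stricter for small patients: at BSA √(158 × 50/3600) = 1.48 m², 60 mL/min/1.73 m² equals 60 × 1.48/1.73 = 51 ml/min. The sponsor should make that change knowingly.

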3.3 Inclusion of Women and Minorities

This trial will not exclude potential subjects from participating in this or any study solely on the basis of ethnic origin, gender or socioeconomic status. Every attempt will be made to enter all eligible patients into this protocol and therefore address the study objectives in a patient population representative of the head and neck cancer population of the catchment area of the MCC.

4. REGISTRATION PROCEDURES

4.1 Protocol Review and Monitoring Committee and Institutional Review Board Review

Before implementing this study, the protocol must be reviewed by Markey Cancer Center's Protocol Review and Monitoring Committee and the protocol, the proposed informed consent form and other information to subjects, must be reviewed by the University of Kentucky Institutional Review Board (IRB). A signed and dated UK IRB initial review approval memo must be maintained in the Markey Cancer Center Clinical Research Office (MCC CRO) regulatory binder. Any amendments to the protocol, other than administrative ones, must be reviewed and approved by the PRMC, study sponsor and the UK IRB.

4.2 Enrollment Guidelines

Eligible patients will be identified by the principal investigator (PI) and co-investigators of this study. Potentially eligible patients will be screened in the University of Kentucky Markey Cancer Center clinics by the investigators, study personnel, and the PI. Upon obtaining proper consent, patients will be enrolled into the study.

4.3 Informed Consent

The goal of the informed consent process is to provide people with sufficient information so they can make informed choices about whether to begin or continue participation in clinical research. The process involves a dynamic and continuing exchange of information between the research

team and the participant throughout the research experience. It includes discussion of the study's purpose, research procedures, risks and potential benefits, and the voluntary nature of participation.

The informed consent document provides a summary of the clinical study and the individual's rights as a research participant. The document acts as a starting point for the necessary exchange of information between the investigator and potential research participant. Also, research participants and their families may use the consent document as an information resource and reference throughout participation in the trial. The informed consent document is often considered the foundation of the informed consent process; it does not, however, represent the entirety of the process. Nor is the informed consent document a risk-management tool for the investigator and/or institution.

The investigator must explain to each subject (or legally authorized representative) the nature of the study, its purpose, the procedures involved, the expected duration, the potential risks and benefits involved and any discomfort it may entail. Each subject must be informed that participation in the study is voluntary and that he/she may withdraw from the study at any time and that withdrawal of consent will not affect his/her subsequent medical treatment or relationship with the treating physician.

This informed consent should be given by means of a standard written statement, written in non-technical language. The subject should read and consider the statement before signing and dating it, and should be given a copy of the signed document. If the subject cannot read or sign the documents, oral presentation may be made or signature given by the subject's legally appointed representative, if witnessed by a person not involved in the study, with documentation that the patient could not read or sign the documents. No patient can enter the study before his/her informed consent has been obtained. The informed consent form is considered to be part of the protocol, and must be submitted by the investigator with the protocol at the time of IRB review.

4.4 Compliance with Laws and Regulations

The study will be conducted in accordance with U.S. Food and Drug Administration (FDA) and International Conference on Harmonization (ICH) Guidelines for Good Clinical Practice (GCP), the Declaration of Helsinki, any applicable local health authority, and IRB requirements. The PI or designee will be responsible for obtaining continuing and not less than annual IRB re-approval throughout the duration of the study. Copies of the PI's annual report to the IRB and copies of the IRB continuance of approval must be maintained by the MCC CRO. The PI or designee is also responsible for notifying the Data and Safety Monitoring Committee of the MCC and the UK IRB of any significant adverse events that are serious and/or unexpected, as per SOP's of those entities. The MCC DSMC will review all adverse events of this IIT as per its SOP.

